## 1.0 INTRODUCTION AND RATIONALE

Several reports suggest that physical activity after cancer diagnosis is associated with better cancer-specific and overall survival in individuals diagnosed with PCa. The role of a healthy diet and sufficient physical activity in cancer prevention have been well documented, and it is widely accepted that a lack of exercise can increase an individual's risk of recurrence or developing new cancers. Increasing attention is now being given to the role of lifestyle in cancer survivorship. There is a growing body of evidence for lifestyle interventions that aim to promote physical activity as having the potential to counter some of the adverse effects of cancer treatments, disease progression and other health outcomes. Exercise performed 2-3 times a week has been shown to improve physical fitness, functional performance, and quality of life in men with PCa; however, few men with PCa exercise regularly and do not meet national physical activity guidelines. A potential explanation on the lack of exercise in men with PCa is the absence of a structured, home-based, exercise program. While studies have shown positive effects of exercise in men with PCa, little is known about how physical activity effects tumor physiology in men with PCa. The primary objective of this pilot study is to gather preliminary data regarding the impact of a novel, home-based exercise program on PCa biomarkers associated with recurrence and metastasis of PCa in men under active surveillance.

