**1.1 Prognostic Biomarkers for PCa Recurrence.** Over the years, many biomarkers have been used for the diagnosis and follow-up of PCa. **PSA** (prostate specific antigen) is the most common marker used, however, recently PSA screening has fallen under controversy based on the high number of false positive diagnosis for PCa. Out of men that display elevated PSA levels in blood, only 25% are associated with PCa. Therefore, other biomarkers need to be studied to more accurately determine the impact of exercise on disease progression. **PSMA**, **EPCA**, **uPA** and **uPAR** are promising PCa markers shed by the tumor that represent the advancement or regression of the prostate tumor that can be quantified in blood. Prostate-specific membrane antigen (**PSMA**) is a type II integral membrane glycoprotein that is overexpressed in the epithelial cells of PCa patients. Literature supports its role in measuring progression of PCa post treatment based on its 94.5% specificity to PCa from other types of malignancy. Early prostate cancer antigen (**EPCA**) is a prostate cancer-associated nuclear structural protein displaying sensitivity and specificity for prostate cancer. In a recent study, EPCA was found to be significantly elevated in localized PCa and strongly predicted cancer progression. Urokinase plasminogen activator (**uPA**) and its receptor (**uPAR**) have been connected with PCa stage and bone metastases. Preoperative plasma uPA was a strong predictor of biochemical recurrence. Elevated levels of both preoperative uPA and uPAR were associated with aggressive biochemical recurrence including development of distant metastasis, suggesting an association with occult metastatic disease. The uPA axis is involved in various phases of tumor development and can be used as a biomarker to determine the effectiveness of exercise in modulating tumor progression. Circulating tumor cells (CTCs) can be quantified through microfiltration and as indicative of advanced prostate cancer and can be an alternative source for disease profiling and

prognostication. While tumor biopsies following an exercise intervention fall outside the scope of current practices in PCa treatment, these biomarkers have the potential to act as circulating biopsy of the tumor.

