Health-Related Quality of Life (SF-36) is designed to assess the health status of patients and has been used previously in this population. The SF-36 assesses eight components of quality of life (physical functioning, role functioning, bodily pain, general health, vitality, social functioning, mental health, and emotional health) that is evidence generated with well-established reliability and validity to support its use.

Functional Assessment of Chronic Illness Therapy-Fatigue (FACIT-F) is a self-reported survey evaluating the impact of fatigue in the patient population. The FACIT-F is a 13 item survey rated on a 5 point scale deemed reliable and valid in measuring fatigue.

**1.4 Rationale for this trial design.** This first of its kind study intends to collect preliminary data on the impact of a home-based exercise program that can improve prognosis, physical function and quality of life in men with PCa; the results of which have the potential to promote health restoration and wellness while reducing cancer

progression in men with PCa. This study will provide data on the feasibility in conducting a home based exercise study and pilot data on the impact of exercise on circulating concentrations of biomarkers reported in the literature to be beneficial for the prognostication of prostate cancer and salivary biomarker for fatigue.

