## **2.0 STUDY OBJECTIVES**

**2.1 Primary Objective:** To demonstrate the impact of a home based exercise program versus wait-list control to modulate circulating prognostic biomarkers PSA, PSMA, EPCA, uPA and uPAR in men with prostate cancer under active surveillance..

2.1.1 Hypothesis: The home based exercise program participants will have significantly lower concentrations of circulating biomarkers compared to their non-exercising counterparts.

**2.2 Secondary Objective:** To determine the impact of a home based exercise program versus wait-list control to modulate a novel salivary biomarker for fatigue in men with prostate cancer under active surveillance.

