## **3.0 STUDY DESIGN**

### **3.1 Description of the protocol**

This study is designed randomized controlled, 2 arm parallel group pilot study.

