## **8.0 STATISTICAL CONSIDERATIONS**

### **8.1 Statistical analysis plan**

Analysis will be done after all participants have completed the 12-week and 24-week timepoints, respectively. The interim analysis at 12-weeks will be for safety and efficacy of the intervention and will include a between group comparison of circulating biomarkers and a review of adverse events reported by study participants.

Statistical analysis will be performed using IBM SPSS 19.0 software. A 2 group analysis of variance (ANOVA) will be used to compare changes in biomarkers, physical function, body composition, body density, and quality of life between the exercise group and the WLC. Pearson's Product Moment Correlation will be used to measure associations between biomarkers in Aim 1 to body composition, body density, physical function and quality of life measured in aim 2. A value of  $p < 0.05$  will be considered statistically significant. The results of this study will be used to calculate power and determine sample size for future research questions in this field.

We will also evaluate the projects procedures and timeline for feasibility. We will document and review our timelines for recruitment for this pilot and ask participants to comment on their experiences in this project with pointed efforts to understand ways to improve the project procedures for effectiveness and efficiency. We will also assess feasibility by documenting and reviewing study patient description described below.

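### Five co-equal primary biomarkers are predicted to be significantly lower at a single p<0.05 threshold with no success rule, which conflicts with the pilot aim; the false-claim rate runs from under 1% to about 12% depending on the reading

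*Combined protocol and SAP*

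**What the plan says.** The primary objective (2.1) is "To demonstrate the impact of a home based exercise program versus wait-list control to modulate circulating prognostic biomarkers PSA, PSMA, EPCA, uPA and uPAR". Its hypothesis (2.1.1) reads: "The home based exercise program participants will have significantly lower concentrations of circulating biomarkers compared to their non-exercising counterparts". The five markers are listed without ranking.

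On analysis, section 8.1 states: "A 2 group analysis of variance (ANOVA) will be used to compare changes in biomarkers". It then sets one general threshold: a p-value below 0.05 "will be considered statistically significant. The results of this study will be used to calculate power and determine sample size for future research questions". Section 8.4 refers to a primary analysis without tying it to a marker or a time point.

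The framing sections describe a different kind of study. Section 1.0 says: "The primary objective of this pilot study is to gather preliminary data regarding the impact of a novel, home-based exercise program on PCa biomarkers". Section 1.4 promises feasibility data and "pilot data on the impact of exercise on circulating concentrations of biomarkers reported in the literature". Section 3.1 calls the design a "2 arm parallel group pilot study".

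Two biomarker comparisons are planned. The one at 12 weeks is called interim and is described in 3.3 and 8.1 as covering efficacy and safety. The other is at 24 weeks, which 7.3.3 calls the end-of-study visit. Nothing says how the 12-week p-values will be read, and week 24 is implied but never named as the main time point for the biomarkers.

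**The concern.** The documents hold two versions of the primary aim. Sections 1.0, 1.4 and 3.1 describe a pilot that gathers data. Sections 2.1.1 and 8.1 together describe a significance test of a directional hypothesis. A pilot can leave multiplicity unadjusted if it says that its p-values are exploratory, but no section here says so.

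The plan also never fixes what would count as support for the primary hypothesis: one marker, several or all five. That choice can therefore be made after the results are seen, and one chance result among five could be reported as support for the hypothesis. Section 8.1 says the results will feed later power and sample-size calculations, so a chance marker could shape the endpoint and the assumed effect of a later trial.

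**Working it through.** The documents give no power, SD, effect size, between-marker correlation or family-wise error rate, so there is no figure of the plan's own to reproduce.

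**Inputs**
- Five primary markers, unranked (2.1).
- Threshold p<0.05 (8.1). Sidedness is not stated. A two-group ANOVA F test is two-sided, so 0.025 falls in the lower direction.
- One test per marker. This is inferred from ANOVA applied to biomarkers; no multivariate test is mentioned.
- 15 men per arm (4.1), all assumed evaluable.
- Common correlation r between markers: not given, so 0 to 0.9 is assumed. Section 1.1 treats uPA and uPAR as linked ("The uPA axis is involved in various phases of tumor development"). That concerns one of the 5×4/2 = 10 pairs, so it does not establish a high correlation across all five.

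**Step 1: independent markers, closed form.** The chance of at least one falsely lower marker is 1 − 0.975^5 = 0.1189, or 11.9%. Counting either direction, it is 1 − 0.95^5 = 0.2262, or 22.6%.

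**Step 2: correlated markers, simulation.** The set-up is no true effect, 24 weeks only, five exchangeable normal markers, a pooled two-sample t-test on each (identical to a two-group ANOVA), two-sided 0.05, and 400,000 replicates per row. The Monte Carlo standard error is about 0.05 percentage points or less.

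| r | at least one lower | exactly one lower | at least two lower | all five lower |
|---|---|---|---|---|
| 0 | 11.9% | 11.4% | 0.6% | 0.00% |
| 0.3 | 10.5% | 8.9% | 1.6% | 0.00% |
| 0.5 | 9.2% | 6.9% | 2.3% | 0.04% |
| 0.7 | 7.6% | 4.7% | 2.9% | 0.19% |
| 0.8 | 6.5% | 3.5% | 3.1% | 0.37% |
| 0.9 | 5.2% | 2.1% | 3.1% | 0.79% |

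A single test gives 2.5%.

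**Step 3: check by integration.** With a normal approximation, the chance of at least one lower marker is 1 − ∫ φ(u) Φ((1.96 − √r·u)/√(1−r))^5 du. This gives 11.9%, 10.5%, 9.1%, 7.4%, 6.4% and 5.1% for the same six values of r, in agreement with the simulation.

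**Step 4: precision of an estimate.** The 95% CI half-width for a between-group difference in change, with 15 per arm, is t(0.975; 28) × √(2/15) = 2.048 × 0.365 = 0.748, or about 0.75 SD. Section 6.0 says that men who discontinue are not replaced, so missing data would widen this.

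**The case against.** The strongest reply is that this is a 30-man pilot and the documents repeatedly say so. The verb 'demonstrate' in 2.1 carries little weight, because 2.3.2 uses the same verb for feasibility. No stopping, treatment or go/no-go decision hangs on p<0.05. This stands, and it limits the severity. What remains is the prediction of significance in 2.1.1 together with the threshold in 8.1. No section labels those p-values exploratory.

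A second reply is that 5-12% needs a rule the documents never state. This also stands. A reader might infer that the plan has an error rate of up to 12%, but the documents do not support that. The hypothesis in 2.1.1 is plural. If at least two markers must be lower, the rate lies on both sides of 2.5%; if all five must be, it is well below. Equally, the plural does not say all five, and 8.1 implements no such rule. The defect is that the reading is left open, not that any one rate is built in.

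A reader might also infer that the 12-week efficacy look inflates the 24-week error. It does not: an earlier comparison leaves the 24-week test as it was. Only if a week-12 result were also allowed to count as support would the any-one rate rise, to about 7-22% under assumed correlations between markers and between looks. The documents do not say that it counts.

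Finally, a reader might conclude that a multiplicity adjustment is required. It is not, if the comparisons are labelled exploratory.

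**Conclusion.** The point holds as an inconsistency and an omission. Five equal-status primary markers and a prediction of significance sit with one unadjusted threshold and no success rule, in a study that elsewhere describes itself as gathering preliminary data. The one-look rate of a false lower claim at week 24 is not a fixed number. Only the any-one reading is above the single-test rate across the whole assumed range; the at-least-two reading passes it from r = 0.7 upwards, and only slightly.

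Confidence is high on the omission, which can be read directly from the text. It is lower on the size, which rests on inferred separate two-sided tests, an assumed common correlation and full follow-up. Severity is minor to moderate: no treatment or stopping decision depends on the result, but what the trial may claim, and what it passes on to later trials, does.

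**What to change.** 1. In 2.1, 2.1.1 and 8.1, label all five biomarker comparisons exploratory. In 2.1, change the verb from demonstrating to estimating the effect. In 2.1.1, say that lower concentrations are expected, without reference to significance. In 8.1, state that no number of p<0.05 results among the five is a confirmatory test of the hypothesis. A sentence covering only a single significant marker would leave two, three or four undefined.
2. In 8.1, name week 24 as the main time point. Report the between-group difference in change, with its SD and 95% CI, for all five markers whatever the p-value, and base future sample-size work on these estimates.
3. In 3.3 and 8.1, state that the 12-week biomarker comparison is descriptive. The adverse-event review stays as it is.
4. Only if the sponsor wants a formal claim: name one primary biomarker at week 24 before any between-group biomarker result is seen, and keep the other four exploratory. That marker is still tested at 0.05, so its power is unchanged: 56% for an assumed standardised effect of 0.8 with 15 evaluable men per arm.

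The cost is wording in four places and one results table, with no new data, visits or participants. The downside is that no formal significance claim can be made on the exploratory markers, nor on any marker at week 12.

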### **8.2 Study patient description**

We will assess the number of participants screened per month and the percentage of screen eligible participants that were randomized into the study. We will assess intervention adherence and participant retention. Adherence will be based on the participant's ability and willingness to perform the prescribed activities. Retention will be defined as percentage of assessments completed. The number of randomized patients will be summarized by age, ethnicity. The number of patients either completing or permanently discontinuing the exercise routine and other interventions will be summarized using counts and percentages.

### **8.3 Clinical Trial Protocol deviations**

All the following deviations will be summarized on the all randomized patient population:

- Inclusion or exclusion criteria not satisfied.
- Deviations related to the interventional arm
- NOTE: A one week window from the scheduled visit is allowed for all visit time periods.

### **8.4 Handling of dropouts or missing data**

All randomized patients will be included in the primary analysis.

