## **6.0 HANDLING OF PATIENT WITHDRAWAL**

Patients may withdraw from the study at any time during the study. Patients may also be withdrawn from the study for not following study related procedures or for the benefit of the patient as determined by study investigators. In the event that a patient withdraws from the study or withdrawn from the study, every attempt should be made to complete the final visit of the study (visit 4 from below). The reason for study discontinuation will be recorded in the subject's folder and case report forms.

All attempts will be made to keep participants in this study. Based on the feasibility aim of this study, the non-compliance guidelines are very lenient. Patients will be withdrawn for non-compliance if they meet any combination of the following: inactivity for 3 consecutive weeks; and/or missing 2 consecutive study appointments where outcome variables are collected.

Patients who discontinue study participation will not be replaced.

In the case study discontinuation is due to an adverse event, such patients will be closely monitored until the resolution or stabilization of this adverse event. This may mean that follow-up will continue after the patient has completed the end of study procedures. Although data on that adverse event will continue to be captured, even beyond the last visit, only those that occur up through the last visit will be recorded.

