2. Download FitBit Data – subjects will be asked to bring the FitBit to this visit so we can download the data that is on the FitBit.
3. Saliva Collection – we will collect about 4 mL of saliva (1/4 of a tablespoon or ¾ teaspoon) to measure FBI concentrations in saliva
4. Body Composition, Body Mass Index and Body Density – will measure body fat percentage by measuring skinfold thickness at 3 sites (chest, abdomen, thigh). We will also measure body mass index by collecting height and weight. Body density will be measured using body fat percentage plus the addition of waist and arm circumference.

7.3.3 Visit 4 (24 week visit; End of Study Visit) – the following activities will be done at the 24 weeks visit (or end of study visit)

1. Blood Draw – we will collect 15 mL of blood (two tubes or 1 tablespoon or 3 teaspoons) to measure circulating markers (PSA, PSMA, EPCA, uPA and uPAR) and circulating tumor cells.
2. Saliva Collection – we will collect about 4 mL of saliva (1/4 of a tablespoon or ¾ teaspoon) to measure FBI concentrations in saliva

3. Surveys for Quality of Life and Fatigue – subjects will be asked to complete 2 surveys that will take about 5 minutes to complete. These surveys are:
  - a. Health-Related Quality of Life (SF-36) – this survey will assess subject's overall health status, including physical functioning, role functioning, bodily pain, general health, vitality, social functioning, mental health and emotional health.
  - b. Functional Assessment of Chronic Illness – Fatigue (FACIT-F) – This survey evaluates the impact of fatigue in men with prostate cancer.
4. Body Composition, Body Mass Index and Body Density – will measure body fat percentage by measuring skinfold thickness at 3 sites (chest, abdomen, thigh). We will also measure body mass index by collecting height and weight. Body density will be measured using body fat percentage plus the addition of waist and arm circumference.
5. 6 minute walk test – we measure overall physical function by asking subjects to walk for 6 minutes. We will track the distance traveled and use this as the post-intervention score.
6. Return Nike FitBit – subjects will be asked to return the Nike FitBit to the research team. Data from the FitBit will be downloaded. After downloading, all data that is on the FitBit will be erased. A summary of the subject's activity can be provided if desired.

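### Section 8.4 keeps every randomised man in the primary analysis, but section 6 can cut short outcome collection for non-compliance, and the change-score ANOVA in 8.1 has no way to use a man without a follow-up value

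*Combined protocol and SAP*

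**What the plan says.** Section 8.4 is headed as the section on dropouts and missing data. Its whole content is "All randomized patients will be included in the primary analysis".

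Section 8.1 names one between-group method: "A 2 group analysis of variance (ANOVA) will be used to compare changes in biomarkers" and the other outcomes. No imputation, repeated-measures model or sensitivity analysis appears. Analyses are planned for weeks 12 and 24.

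Section 6 first gives a discretionary rule: "Patients may also be withdrawn from the study for not following study related procedures". It then makes withdrawal for non-compliance mandatory on any combination of "inactivity for 3 consecutive weeks; and/or missing 2 consecutive study appointments where outcome variables are collected". Withdrawn men are not replaced.

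Three statements soften this:

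- Section 6 says of its own rules: "Based on the feasibility aim of this study, the non-compliance guidelines are very lenient".
- After any withdrawal, section 6 says "every attempt should be made to complete the final visit of the study (visit 4 from below". Section 7.3.3 includes the biomarker draw at that visit.
- Section 8.2 reports retention as the percentage of assessments completed, and separately counts men who permanently stop the exercise routine.

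On the timing of visit 4, section 7.3.3 says "the following activities will be done at the 24 weeks visit (or end of study visit". Section 8.3 allows one week either side of a scheduled visit.

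**The concern.** A change score needs a baseline and a follow-up value. A man without the second cannot enter the ANOVA, so 8.4 cannot be carried out for him. One such man is enough, whatever the loss rate.

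Section 6 can add to the missing data through a rule tied to adherence. If men who stop exercising also have worse biomarker changes, and more of them are lost from the exercise arm, the remaining comparison leans towards exercise. Separately, if a withdrawn man is sampled when he leaves and the value is analysed as week 24, the 24-week contrast mixes different lengths of follow-up.

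This is a 30-man pilot, so the stake is less a wrong treatment decision than a shifted estimate that is carried forward: 8.1 says the results will be used to size future studies.

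**Working it through.** **What the rule costs.** Outcome visits after baseline are at weeks 12, 18 and 24 (7.3). The documents describe no contact between baseline and week 12. FitBit data are collected at visits 2 and 3: "subjects will be asked to bring the FitBit to this visit so we can download the data that is on the FitBit". Inactivity would therefore probably first be seen at week 12 or 18. This is an inference: exercise men also keep a record of completed exercises (5.1), which might reveal it sooner.

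| Trigger | Value in hand | Still sought under section 6 | Lost or in doubt because of the rule |
|---|---|---|---|
| Inactivity seen before week 12 | baseline | visit 4 | weeks 12 and 18; timing of visit 4 |
| Inactivity seen at week 12 | week 12 | visit 4 | week 18; timing of visit 4 |
| Inactivity seen at week 18 | weeks 12 and 18 | visit 4 | timing of visit 4 |
| Weeks 12 and 18 missed | baseline | visit 4 | timing of visit 4 only; no post-baseline value if visit 4 fails |
| Weeks 18 and 24 missed | week 12 | none left | nothing further |

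An exit sample at week 12 is 24 − 12 = 12 weeks early, and one at week 18 is 24 − 18 = 6 weeks early, against a one-week window.

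**Bias from lost values.** From the documents: 15 men per arm (4.1). Assumed: no true effect; SD of change 1; the k least compliant exercise men have no follow-up value; no controls are lost; correlation ρ between non-compliance and a worse change.

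Bias = ρ × S / (15 − k), where S is the sum of the k largest expected values in a standard normal sample of 15 (1.736, 1.248, 0.948, 0.715, 0.516).

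- k = 1, ρ = 0.3: 0.3 × 1.736 / 14 = 0.037 SD
- k = 3, ρ = 0.3: 0.3 × 3.932 / 12 = 0.098 SD
- k = 3, ρ = 0.5: 0.5 × 3.932 / 12 = 0.164 SD
- k = 5, ρ = 0.3: 0.3 × 5.162 / 10 = 0.155 SD
- k = 5, ρ = 0.5: 0.5 × 5.162 / 10 = 0.258 SD

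Simulation (400,000 trials per case) agrees. The nominal 5% two-sided error becomes about 5.2% for k = 1 at ρ = 0.3, 5.7% for k = 3 at ρ = 0.3, and 9.7% for k = 5 at ρ = 0.5. With two exercise men and one control lost at ρ = 0.3, the bias is 0.03 SD. With ρ = 0, or with equal loss of the same pattern in both arms, it is zero.

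For scale, the standard error of the difference with complete data is √(2/15) = 0.37 SD, larger than every bias above.

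**What visit 4 recovers.** For k = 5 and ρ = 0.5, obtaining three of the five samples cuts the bias to 0.08 SD if a random three return, or 0.115 SD if the three least non-compliant return.

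**What a repeated-measures model recovers.** Suppose the lost men keep a week-12 value but lack weeks 18 and 24, and changes at weeks 12 and 24 correlate 0.5 to 0.7 (assumed). For k = 3 to 5 and ρ = 0.3 to 0.5, the ANOVA bias is 0.10 to 0.26 SD and the repeated-measures bias is 0.03 to 0.14 SD. About half remains at correlation 0.5 and a third at 0.7.

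**Exit sample used as week 24.** With no time trend and the same link to non-compliance at both weeks, this causes no bias. If values shift by 0.3 SD between exit and week 24 (assumed) and five exercise men are affected, the bias is (5/15) × 0.3 = 0.10 SD. Its direction depends on the trend.

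**The case against.** The strongest reply is that section 6 costs little. Visit 4 is sought after every withdrawal, and two missed visits leave at most visit 4 to collect. On the likely timing of detection, the rule mainly removes the week-18 value, and 8.1 names only weeks 12 and 24 for analysis. The larger simulated biases describe men with no follow-up value, most of whom would have missed visits themselves; changing section 6 would not bring them back. An early exit sample is also not always harmful, as the no-trend case shows. All of this stands, and it limits the size of the point.

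Four stronger readings are tempting, and the documents do not support them:

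- **Outcome collection stops at withdrawal.** The request for visit 4 says otherwise.
- **The two descriptions of visit 4 contradict each other.** They agree for a man who completes the study. They are ambiguous only for a withdrawn man. Section 6 also speaks of adverse-event follow-up continuing after end-of-study procedures, which makes an early exit visit a natural reading but does not settle it.
- **The rule falls on the exercise arm only, so bias towards exercise is certain.** Both arms wear a FitBit (7.3.1) and the rule names no arm. Inactivity is undefined and only the exercise arm has a prescription, so greater use there is plausible, no more.
- **Keeping the planned visits would remove the bias.** That holds only if everyone attends.

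The reply does not answer the absence of any method in 8.4, the open timing of visit 4, or the unsought visits.

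**Conclusion.** The point holds in a limited form and should be corrected. That 8.4 cannot be carried out with the 8.1 test for a man without a follow-up value follows from the text and needs no assumption. Section 6 adds to the problem by not seeking the remaining visits before visit 4 (mainly week 18, or week 12 if inactivity is found earlier) and by leaving open whether visit 4 is at exit or at week 24.

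The size is uncertain and probably modest. Loss rate, difference between arms and correlation with outcome are all assumed; the illustrated 0.04 SD and 0.10 to 0.26 SD also assume that no visit-4 sample is recovered and no control is lost. The upper end is an extreme case, and much of that loss would not be caused by section 6. Confidence in the textual gap is high; confidence in the size is low.

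**What to change.** 1. **Sections 6 and 8.4.** Reconcile them so that non-compliance alone does not end outcome collection. Consenting men keep their remaining planned week-12, 18 and 24 visits, with visit 4 sought at week 24, and are analysed in their randomised arm. Withdrawal by the man's own choice or for his benefit is unchanged. This prevents loss caused by the rule; it does not recover men who miss visits or leave by choice.
2. **Section 8.1.** For the biomarkers, replace the change-score ANOVA with a baseline-adjusted repeated-measures model on the planned post-baseline values, with the 24-week arm contrast as primary (the sponsor to confirm the time point). Men with a week-12 or week-18 value then contribute. Some bias remains.
3. **Early exit samples.** Analyse them at their actual week or in a sensitivity analysis, not as week-24 values.
4. **Sections 8.2 and 8.4.** Report missing values by arm and visit, and state that men with no post-baseline value are counted but cannot inform the contrast.

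The cost is wording and slightly more analysis work. No visit or sample is added, since all three draws are already planned. The sponsor should confirm that the model runs in the named software. The downside is that staff keep scheduling visits for men who have stopped exercising.
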